Efficacy of near-assisted learning (NAL) in improving students' OSCE grades: A single-blinded RCT

Document date: 10/4/2019

Study protocol:

In this single-blinded randomized controlled trial, 1st year male medical students of Sulaiman Alrajhi Colleges were invited via emails to participate voluntarily. Forty-eight students agreed to join and, after informed consent, were randomly assigned to one of two groups; the near-assisted learning group (The intervention) and the self-directed learning group (The control arm). Meanwhile, a group of 5th year medical students, known to be the top in their class, were invited to participate as instructors during the OSCE sessions. After their acceptance, they underwent extensive 2-week crash course focusing in basics of medical education, teaching and feedback cycle, along with quick supervised revision of systemic and general physical examination. At the analysis phase, scores of the previous batch were also included as a 3rd group for comparison. The study was concluded after 9 days, when the students had their skills evaluated during OSCE examination.

Analysis plan:

Through SPSS 23rd edition, frequency, proportion analysis, chi-square and Fisher's exact test were used. A probability value of less than .05 was determined for significance.

Results:

Those scoring B or better in the near-assisted learning, self-directed learning and the students of the previous batch groups were 22 (88%), 19 (82.6%) and 7 (50%), respectively ($p= 0.025$). More participants from the last group score A or more in comparison to the other two groups. On the other hand, less students failed the OSCE exam from the near-assisted and self-directed learning groups than the group of the prior batch.

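### Does sharing student instructors in the near-assisted learning arm invalidate the planned chi-square and Fisher tests?

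*Combined protocol and SAP*

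**What the plan says.** Individual students "were randomly assigned to one of two groups": NAL, or a self-directed learning (SDL) control for which no teacher is described. The teaching side is covered in a single sentence: high-ranking 5th-year students "were invited to participate as instructors during the OSCE sessions". These instructors had two weeks of training. The number of instructors, the size of the teaching groups and the pairing of students with instructors are not stated. Nor does the text say outright which arm they taught, although NAL is the natural reading.

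The Analysis plan lists its methods as "frequency, proportion analysis, chi-square and Fisher's exact test were used", at a 5% threshold. It has no term for instructor or teaching group.

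The Results section gives those scoring B or better in NAL, SDL and the previous batch as "22 (88%), 19 (82.6%) and 7 (50%), respectively", with one p-value of 0.025.

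**The concern.** Randomising individuals makes the arms comparable at baseline, but it does not keep outcomes independent once a shared teacher has acted on several students. If each NAL student belonged to one instructor's set while SDL students had none, the trial would be partially nested, with clustering in one arm only. Both named tests assume independent students. With positive correlation within instructors, the NAL variance would be understated, and p-values and intervals for NAL against SDL would look too precise.

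This bears on the aim of the trial. The title is about NAL as a method, so inference should extend beyond the few selected students who taught it. A usual remedy would be a mixed model with an instructor effect in the NAL arm, or a sensitivity analysis that inflates the NAL variance.

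**Working it through.** **Inputs from the document.** "Forty-eight students agreed to join". Denominators follow from the Results: 22/0.88 = 25 (NAL), 19/0.826 = 23 (SDL), 7/0.50 = 14 (previous batch); 25 + 23 = 48.

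**Inputs assumed.** Number of instructors k and ICC are not given. The main illustration takes k = 5 with m = 5 students each; the wider range is k = 2 to 8 with m = 25/k. ICC runs from 0.05 to 0.20 in both.

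**1. Reproduce the stated p-value.** For the 3×2 table 22/3, 19/4, 7/7, the Fisher-Freeman-Halton exact test gives p = 0.0254, which rounds to the stated 0.025. (Pearson chi-square is 7.976 on 2 df, p = 0.0185.) The reported figure is therefore a three-group test that includes the non-randomised previous batch.

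**2. The randomised comparison, unadjusted.** The difference is 0.880 − 0.826 = 0.054.

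- Variance: 0.88 × 0.12/25 + 0.826 × 0.174/23 = 0.00422 + 0.00625 = 0.01047, so SE = 0.102.
- 95% CI: 0.054 ± 1.96 × 0.102, that is −14.7 to 25.4 points.
- Fisher p = 0.70; uncorrected chi-square p = 0.60.

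**3. Allow for clustering in NAL only, k = 5.** The design effect is DE = 1 + (m − 1) × ICC = 1 + 4 × ICC, which is 1.2 at ICC 0.05 and 1.8 at ICC 0.20.

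- Under a common proportion, the variance ratio is V = (DE/25 + 1/23)/(1/25 + 1/23), so √V = 1.05 to 1.18.
- Approximate type I error is 2[1 − Φ(1.96/√V)] = 6.1% to 9.6%.
- The interval in step 2 becomes −15.5 to 26.2 points at DE 1.2 (SE 0.106) and −17.7 to 28.5 at DE 1.8 (SE 0.118).

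**4. Size of the two named tests.** The formula in step 3 describes a z-test or uncorrected chi-square, not Fisher. Exact enumeration used a beta-binomial NAL arm (5 × 5), a binomial SDL arm of 23, and a common proportion of 41/48 = 0.854:

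| ICC | Uncorrected chi-square | Fisher |
|---|---|---|
| 0 | 5.0% | 3.2% |
| 0.05 | 6.0% | 4.2% |
| 0.10 | 7.1% | 5.2% |
| 0.20 | 9.4% | 7.3% |

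Seven of the 48 fell below B, so the expected counts in those cells are 25 × 7/48 = 3.6 and 23 × 7/48 = 3.4. Both are under 5, which makes Fisher the natural choice for this table.

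**5. Effect on the results, k = 2 to 8, ICC 0.05 to 0.20.** DE runs from 1.11 to 3.30, and the approximate type I error of step 3 from 5.6% to 17.6%. Dividing the NAL counts by DE and retesting with Pearson chi-square:

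- NAL against SDL: p = 0.61 to 0.73.
- Three groups: p moves from 0.0185 to between 0.021 and 0.057. Of the combinations tried in this range, only k = 2 with ICC 0.20 passes 0.05.

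**The case for a change.** The best case for acting is that the principle is right and the cost small. Teaching skill was part of what the instructors were trained in, so differences between them are plausible. Chi-square is also named in the plan and lacks Fisher's cushion. Even Fisher exceeds 5% at ICC 0.20, and it would do worse with two or three instructors. Intervals matter for a null result too: with 4 instructors and ICC 0.10 (DE 1.525) the NAL − SDL interval widens to −16.7 to 27.5 points.

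All of that stands as conditional reasoning. What does not stand is the step from there to a required model. Fixed teaching sets are not documented, and if students rotated among instructors the simple test would be reasonable. A partially nested model would estimate an instructor variance from perhaps five sets of about five students, which is barely feasible. It would need student-instructor records that the document does not mention. Run on the OSCE score, it would also replace the graded outcome that the Results report. Statisticians would differ on whether that improves on a simple exact test here. Nor is there a reported NAL-against-SDL p-value or interval that could be overstating the evidence.

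**Conclusion.** No change to the plan. The documented part of the concern is an omission: the number of instructors and the pairing with students are not given. One line in the report stating both would be useful to readers, but the analysis does not depend on it.

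The statistical harm rests on assumed fixed sets and an assumed ICC. In the 5 × 5 layout it amounts to a size of 6.0% to 9.4% for uncorrected chi-square and 4.2% to 7.3% for Fisher, against a nominal 5%. Fewer instructors would make it larger and rotation smaller. In no case examined does the reading of the randomised comparison change: the difference is 5.4 points and p stays above 0.6. The 0.025 comes from a comparison that includes the non-randomised previous batch, a separate matter that modelling instructors would not resolve.

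### The previous batch, added as a third group at analysis without randomisation or a stated entry rule, carries the only p-value and the failure statement, so neither can be credited to near-assisted learning

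*Combined protocol and SAP*

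**What the plan says.** The Study protocol section gives the entry route for the trial arms: "1st year male medical students of Sulaiman Alrajhi Colleges were invited via emails to participate voluntarily". It continues: "Forty-eight students agreed to join and, after informed consent, were randomly assigned to one of two groups". The two groups are near-assisted learning (intervention) and self-directed learning (control).

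The third group appears later in the same section: "At the analysis phase, scores of the previous batch were also included as a 3rd group for comparison". No invitation, consent, eligibility rule, selection method or size is given for it.

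The Analysis plan section says that "frequency, proportion analysis, chi-square and Fisher's exact test were used" and adds: "A probability value of less than .05 was determined for significance". It does not say which groups are to be compared, or that the randomised contrast is the main one.

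The Results section gives the numbers scoring B or better in the near-assisted, self-directed and previous-batch groups as "22 (88%), 19 (82.6%) and 7 (50%), respectively", with a single p-value of 0.025. It then makes two statements without counts. One is that the group named last did best on the share or number scoring A or above. The other is that "less students failed the OSCE exam from the near-assisted and self-directed learning groups than the group of the prior batch".

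**The concern.** Randomisation protects one comparison here, near-assisted against self-directed. A comparison with the previous batch has no such protection. That group sat its exam in another year, did not come through this trial's invitation and consent, and was brought in at the analysis stage by a rule the document does not give. Any difference from it may come from who volunteered, the school year, the exam or its marking, or which students make up the group.

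The previous batch is nevertheless analysed alongside the trial arms as though it were a third arm. If the only p-value and the only statement about failures both lean on it, a reader of a document whose title announces the efficacy of near-assisted learning may take a difference between years for an effect of the teaching.

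**Working it through.** **Inputs** (Results section): 22 (88%), 19 (82.6%), 7 (50%), p = 0.025. From the Study protocol section: 48 students randomised.

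**Step 1. Group sizes.** The size is the count divided by the stated proportion. Each has one whole-number solution.

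- Near-assisted: 22 / 0.88 = 25
- Self-directed: 19 / 0.826 = 23
- Previous batch: 7 / 0.50 = 14

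Check: 25 + 23 = 48, the number randomised.

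**Step 2. Reproduce the stated p-value.** The three groups total 25 + 23 + 14 = 62 students, of whom 22 + 19 + 7 = 48 scored B or better (by coincidence also the number randomised). With both margins fixed, the probability of a table with a, b and c such students is

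P(a, b, c) = C(25, a) × C(23, b) × C(14, c) / C(62, 48), with a + b + c = 48.

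The Fisher-Freeman-Halton p-value sums P over every table no more probable than the observed (22, 19, 7). The result is 0.0254, which matches the stated 0.025. On the same table, Pearson chi-square is 7.98 on 2 df (p = 0.0185) and the likelihood-ratio test gives p = 0.0269. The stated value is therefore the exact three-group test, with the previous batch included.

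**Step 3. Separate the contrasts** (B or better, two-sided Fisher exact test).

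| Contrast | Rates | Difference | p |
|---|---|---|---|
| Near-assisted vs self-directed (randomised) | 88.0% vs 82.6% | 5.4 points | 0.70 |
| Near-assisted vs previous batch | 88.0% vs 50.0% | 38.0 points | 0.019 |
| Self-directed vs previous batch | 82.6% vs 50.0% | 32.6 points | 0.06 |

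The randomised difference has a 95% Newcombe interval of −15.4 to +26.6 points. The small three-group p-value thus comes from the gap between the previous batch and the trial arms.

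**Step 4. Precision of the third group.** The exact (Clopper-Pearson) 95% interval for 7/14 is 23% to 77%. With 8/14 in place of 7/14, the three-group exact p rises from 0.025 to 0.095. One student's grade therefore moves the result across the 0.05 level. This reflects the small group and is not evidence of how it was chosen.

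**Step 5. The failure statement.** No failure counts, percentages or test are given, so it cannot be recomputed. With unequal groups (25, 23 and, if the same students are meant, 14), it is also unclear whether the statement concerns numbers or proportions.

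**The case against.** The fairest defence is that the document does not hide what it did. It says that the previous batch was added at analysis, it names only two randomised groups, and its failure sentence describes both arms together without crediting tutoring. A historical group can be useful context. That much stands. However, the single p-value covers all three groups, and no result is given for the randomised contrast alone.

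A reader might also infer more than the text supports.

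- *That the previous batch were non-volunteers, or the 14 a chosen subset.* No entry rule is given. The 14 could be the whole batch, part of it, or students who agreed to release scores. What is known is that they were not randomised in this trial and that the rule is unstated.
- *That the volunteers were simply stronger or more motivated students.* This is plausible but undocumented. The sentence about grade A or above complicates it: in the order listed, the last group is the previous batch, which on that reading did better at the top grade. It is not clearly worse on every grade.
- *That most of the gap is proved to be unrelated to tutoring.* The point estimates lean that way (32.6 of 38.0 points is about 86%), but this is a ratio of two imprecise differences and should not be quoted as an established share.
- *How large any volunteer bias is.* The document gives no class size and no grades for non-volunteers, so this cannot be estimated.

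**Conclusion.** The point stands as one of attribution. The previous batch is a non-randomised group, added at analysis with no stated entry rule and a derived size of 14, and the reported p-value of 0.025 depends on it. Neither that p-value nor the failure statement can be credited to near-assisted learning. The randomised evidence is 22/25 against 19/23, whose interval is wide enough to include a sizeable effect in either direction. It therefore shows neither a benefit nor the absence of one.

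Two assumptions are used. The group sizes are those implied by the B-or-better percentages, which the match to 48 randomised and to the stated p-value supports. Applying 14 to the failure statement assumes the same denominator, which the document does not confirm. The direction and size of any bias in the previous-batch contrast are unknown.

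**What to change.** 1. In the Study protocol and Results sections, remove the previous batch as a study group, and take it out of the significance test.
2. In the Analysis plan section, name near-assisted against self-directed as the comparison to be tested. Report it in Results as 22/25 against 19/23: difference 5.4 points, 95% interval −15.4 to +26.6, Fisher p = 0.70.
3. Delete the failure sentence, or replace it with failure counts for each randomised arm.
4. If previous-batch figures are kept, show them apart from the trial results as descriptive, non-randomised context. State the rule for who is included and the group size, give no p-value, and draw no conclusion from them about either learning method.

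The cost is rewording, one recomputed test and, if item 3 is met by replacement, a count of failures per arm. No new students or procedures are needed. The downside is that the significant p-value and the favourable contrast with the previous batch are lost, leaving an inconclusive randomised result.

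### An ordered OSCE grade is analysed only with tests that ignore order; in the randomised comparison, under stated assumptions, Fisher's test on B or better loses about 39–56% of a rank test's power

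*Combined protocol and SAP*

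**What the plan says.** The title gives the aim: "Efficacy of near-assisted learning (NAL) in improving students' OSCE grades". The Analysis plan names its methods in one sentence: "frequency, proportion analysis, chi-square and Fisher's exact test were used". The threshold follows: "A probability value of less than .05 was determined for significance". It states no sidedness, no cut-point on the grade, and no method that uses the order of the grades.

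The Study protocol section adds a non-randomised group: "At the analysis phase, scores of the previous batch were also included as a 3rd group for comparison".

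Results gives one tested comparison, with p = 0.025. The counts at B or better "were 22 (88%), 19 (82.6%) and 7 (50%), respectively"; the order is NAL, self-directed learning, previous batch. Two other parts of the grade scale appear in words only, with no counts and no test: "More participants from the last group score A or more in comparison to the other two groups", and "less students failed the OSCE exam from the near-assisted and self-directed learning groups than the group of the prior batch". The full grade distribution is not shown.

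**The concern.** A letter grade running from A down to fail carries more information than whether it reached B. Chi-square and Fisher's exact test treat grades as unordered labels. If the grade is first split at B, the difference between A and B is lost, and so are all differences below B.

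The cut also lies where there is little room to improve. In the self-directed arm 82.6% already reach B, so NAL can add at most 100 - 82.6 = 17.4 points on this measure. With the sample fixed at 48 volunteers, the choice of analysis is one of the few remaining ways to gain precision on the randomised question.

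**Working it through.** **Inputs from the document.** The percentages imply the denominators: 22/0.88 = 25, 19/0.826 = 23 and 7/0.50 = 14. The first two sum to 48, the number randomised. Alpha is .05, taken as two-sided.

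**Reproducing the printed p-value.** On the 3 × 2 table (22/3, 19/4, 7/7), the Fisher-Freeman-Halton exact test gives p = 0.0254. Uncorrected Pearson chi-square is 7.98 on 2 df, p = 0.0185. The printed 0.025 therefore fits the exact test run on the B-or-better split with all three groups.

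**The randomised comparison on the same split.** The difference is 22/25 - 19/23 = 0.880 - 0.826 = 0.054. Newcombe's 95% CI is -15.4 to +26.6 points, and Fisher p = 0.70.

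**Power: assumptions not in the document.** Latent score normal; NAL shifts it by d SD; 25 against 23; control P(B or better) = 0.826, as observed; five grades, with control cumulative shares of 82.6%, 92% and 96% from the top down to each grade from B; control share at A varied from 5% to 40%.

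Under NAL, P(B or better) = Φ(Φ⁻¹(0.826) + d), which is 0.925 at d = 0.5 and 0.959 at d = 0.8. Power on the split is an exact sum over Binomial(25) × Binomial(23). Rank-test power (tie-corrected Mann-Whitney) is simulated with 100,000 replicates. Fisher's exact test on all five grades (Freeman-Halton) uses 8,000 replicates.

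| Test | A share | Power, 0.5 SD | Power, 0.8 SD |
|---|---|---|---|
| Fisher, split | any | 0.1525 | 0.2875 |
| Chi-square, split | any | 0.170 | 0.298 |
| Rank test, grades | 5% | 0.250 | 0.547 |
| | 10% | 0.287 | 0.609 |
| | 20% | 0.316 | 0.653 |
| | 26% | 0.320 | 0.657 |
| | 40% | 0.315 | 0.634 |
| Freeman-Halton, grades | 5% | 0.135 | 0.344 |
| | 10% | 0.187 | 0.441 |
| | 20% | 0.222 | 0.497 |
| | 40% | 0.221 | 0.490 |

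Relative loss = 1 - power(test)/power(rank test).

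- Fisher on the split, 0.5 SD: from 1 - 0.1525/0.250 = 39% to 1 - 0.1525/0.320 = 52%.
- Fisher on the split, 0.8 SD: from 1 - 0.2875/0.547 = 47% to 1 - 0.2875/0.657 = 56%.
- Other shifts: 30–41% at 0.24 SD and 50–52% at 1.2 SD.

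**Is this only Fisher's conservatism?** Type I error is 0.034 for Fisher on the split, 0.052 for chi-square on the split and 0.048–0.051 for the rank test. Chi-square on the split, close to nominal size, still loses 32–47% at 0.5 SD and 45–55% at 0.8 SD.

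**Favourable reading: the planned tests run on all five grades.** From the table, Freeman-Halton loses about 30% (1 - 0.222/0.316) to 46% (1 - 0.135/0.250) at 0.5 SD. At 0.8 SD it loses 23% (1 - 0.490/0.634) to 37% (1 - 0.344/0.547). Five-level chi-square loses 54–69% and 40–55%.

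**Control rate.** The exact 95% CI for 19/23 is 61% to 95%. At 0.8 SD, Fisher's loss on the split is 30–35% at a rate of 61%, 35–41% at 70% and 73–80% at 90%. The cuts chosen below B matter little: alternatives give 38–52% and 47–56%.

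**Information.** For a small normal shift the split carries φ(z)²/[p(1 - p)] = 0.459, with p = 0.826 and z = Φ⁻¹(p). The five-level grade carries 0.651 (A = 5%) to 0.826 (A = 30%). The split therefore keeps 0.459/0.826 = 56% to 0.459/0.651 = 71% of the grade's information, equivalent to about 27–34 of the 48 students. Against an assumed normal numeric score it keeps about 46% (22–62% over the control-rate CI).

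**The case against.** The plan commits to no cut-point, and a short Results section with one p-value does not prove that nothing else was tested. The 39–56% figure is for a two-arm test on the split, which the document does not report. This stands as a limit on scope. If the planned exact test was run on all grades, the loss is the smaller one shown above. For the three-group test, with shifts matched to the observed rates, the loss against Kruskal-Wallis is only about 16–18%. The two-arm contrast is nevertheless the one that randomisation supports.

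The range also depends on assumed grade shares and on a control rate taken from the trial's own results. This stands too, so the assumptions must be printed with the figure.

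The absolute gain is small near the observed effect. The 5.4 points correspond to about 0.24 SD, where Fisher has about 7% power and the rank test 9–11%. No analysis makes 48 students decisive.

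The strongest objection is that a pure shift is unverified. If NAL only moves students across the B border and leaves the A share alone, the split is the better test: at A = 20%, Fisher has 15% and 29% power against 9% and 12% for the rank test. If NAL only raises the A share, the split has 3% power against 15% and 33%. Nothing in the document suggests an effect confined to the B border. Read naturally, Results gives the previous batch both more A grades and more failures, which is not a shift. That group was not randomised, so the pattern says nothing about a shift between the two arms.

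**Conclusion.** The concern holds. Two parts are facts of the document: only order-ignoring tests are named for an ordered outcome, and the only printed p-value is for B or better across three groups, one of them not randomised.

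The size is conditional. The 39–56% relative loss, for the randomised comparison at 0.5–0.8 SD, rests on a latent-normal shift, five grades, 5–40% of controls at A, and 82.6% of controls at B or better. Over control rates of 61–90% the loss at 0.8 SD runs from 30% to 80%. Confidence is moderate, because the document gives no grade distribution against which to check these inputs. The change should be made; it adds precision but does not rescue a small trial.

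**What to change.** Compare NAL with self-directed learning on the full ordered grade by a two-sided Wilcoxon-Mann-Whitney test. Report the probability that a NAL student has the higher grade, ties counted half, with its 95% CI. Tabulate every grade by arm. Keep B or better as a descriptive secondary result, with the difference and 95% CI for the two randomised arms. If numeric scores are held for both arms, also report the mean difference with 95% CI. Label all of this post hoc, since results are already reported.

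The cost is a change of wording and one standard procedure on recorded grades. The probability measure equals the area under the ROC curve, so its interval is also standard. The mean difference needs numeric scores, which the document implies but does not show. There are three drawbacks: the effect measure is less familiar than a percentage, a post hoc analysis carries less weight, and power is lost if NAL acts only at the B border.

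### The planned inference is a p-value alone: no effect estimate or confidence interval is planned or reported for near-assisted versus self-directed learning

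*Combined protocol and SAP*

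**What the plan says.** Under Study protocol, "Forty-eight students agreed to join and, after informed consent, were randomly assigned to one of two groups". The two arms are "the near-assisted learning group (The intervention) and the self-directed learning group (The control arm"). At the analysis stage, "scores of the previous batch were also included as a 3rd group for comparison"; these earlier students were not randomised.

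The Analysis plan states that "frequency, proportion analysis, chi-square and Fisher's exact test were used", followed by the decision rule "A probability value of less than .05 was determined for significance". It contains no other analysis instruction. No difference, ratio or confidence interval is named, and no contrast between the two randomised arms is specified.

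The Results give the share scoring B or better in NAL, self-directed learning and the previous batch as "22 (88%), 19 (82.6%) and 7 (50%), respectively", with a single p-value of 0.025 for the three groups. Statements about grade A and about failing the examination follow in words only, without counts.

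**The concern.** The title asks whether NAL improves examination grades, and the trial was randomised to answer that against self-directed learning. That is a question about the size of a difference and how well it is known. Group percentages plus a significance rule do not supply either as a stated result: no figure is planned for the gap between the two randomised arms, and nothing conveys its precision.

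What is at stake is how the one reported p-value will be read. In a document titled as a randomised trial of NAL, a value of 0.025 next to an 88% success rate is easily taken as evidence for NAL. If it actually comes from a three-group test that includes the previous batch, it carries no specific information on NAL against its control. An estimate with an interval for the randomised contrast would prevent that reading.

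**Working it through.** **Inputs, all from the Results and Study protocol.** Counts at B or better: 22, 19 and 7. Percentages: 88, 82.6 and 50. Number randomised: 48.

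**Step 1: denominators (derived, not stated).** 22/0.88 = 25; 19/0.826 = 23.0; 7/0.50 = 14. Check: 25 + 23 = 48, the number randomised.

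| Group | B or better | Below B | Total |
|---|---|---|---|
| NAL | 22 | 3 | 25 |
| Self-directed | 19 | 4 | 23 |
| Previous batch | 7 | 7 | 14 |
| All | 48 | 14 | 62 |

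**Step 2: reproduce the reported p-value.** The smallest expected count is 14 × 14/62 = 3.16, so an exact test is the natural choice.

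| Test | p |
|---|---|
| Three groups, Fisher (Freeman-Halton) exact | 0.0254 |
| Three groups, Pearson chi-square (7.98, 2 df) | 0.0185 |
| Three groups, likelihood ratio | 0.027 |
| NAL v previous batch, Fisher | 0.019 |
| NAL v previous batch, continuity-corrected chi-square | 0.026 |
| Self-directed v previous batch, Fisher | 0.063 |
| Both randomised arms pooled v previous batch, Fisher | 0.010 |
| **NAL v self-directed, Fisher** | **0.70** |
| **NAL v self-directed, uncorrected chi-square** | **0.60** |

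Of the tests tried, only the three-group exact test rounds to 0.025. Neither test of the randomised contrast comes near it.

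**Step 3: the estimate that is not reported.** Difference = 22/25 − 19/23 = 0.880 − 0.826 = +0.054, or +5.4 percentage points.

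**Step 4: its 95% interval by Newcombe's method.** The Wilson score limits are 0.700 to 0.958 for 22/25 and 0.629 to 0.930 for 19/23. With d the difference, p the observed proportions, and l and u the Wilson limits (1 = NAL, 2 = self-directed):

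- Lower = d − √[(p1 − l1)² + (u2 − p2)²] = 0.054 − √[(0.880 − 0.700)² + (0.930 − 0.826)²] = 0.054 − 0.208 = −0.154
- Upper = d + √[(u1 − p1)² + (p2 − l2)²] = 0.054 + √[(0.958 − 0.880)² + (0.826 − 0.629)²] = 0.054 + 0.212 = +0.266

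**Step 5: sensitivity to the method.**

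| Method for the difference | 95% CI, percentage points |
|---|---|
| Newcombe | −15.4 to +26.6 |
| Score | −16.6 to +28.4 |
| Agresti-Caffo | −15.4 to +25.8 |
| Wald | −14.7 to +25.4 |

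On ratio scales, the risk ratio is 0.880/0.826 = 1.07 (log method 0.84 to 1.35; score 0.82 to 1.43). The odds ratio is (22 × 4)/(3 × 19) = 1.54 (logit 0.31 to 7.79; score 0.33 to 7.10). Every interval includes both benefit and harm.

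**Step 6: the other grade cuts.** The Results give no counts for A or better or for failure, so neither a difference nor an interval can be derived for them.

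**The case against.** The strongest reply is that the omission is one of presentation. Counts and percentages are printed for both randomised arms, so a reader can work out the +5.4 points and an interval. That stands for B or better, although the denominators must be back-calculated. It does not stand for A or better or for failure, where no counts are given.

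A reader might infer that the missing interval is what stops the trial from ruling out harm. The arithmetic does not support this. The interval reaches about −15 points, so reporting it would not exclude harm either; that limit comes from having 25 and 23 students. Likewise, the size of the difference is recoverable for B or better, so it would be wrong to say that the trial cannot yield one.

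A reader might also infer that the Results present the two arms as equally good, because they are named together where "less students failed the OSCE exam from the near-assisted and self-directed learning groups than the group of the prior batch". That sentence sets each arm against the previous batch and makes no claim about NAL relative to self-directed learning. Nor do the documents report a null p-value that could be mistaken for equivalence. The only p-value is a significant one, so the present risk is false credit to NAL.

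Finally, one could say that the real fault is the third group. It is a related fault, but removing the previous batch would leave a bare p = 0.70, still without an estimate or interval.

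**Conclusion.** The point holds as a reporting improvement worth making. No between-arm estimate or interval is planned or reported for the comparison that was randomised, and the one p-value given does not isolate that comparison. On the derived counts, NAL minus self-directed learning is +5.4 percentage points at B or better, with a 95% interval of about −15 to +27. The randomised data are compatible with NAL lowering that share by about 15 points or raising it by about 27, so they are inconclusive on efficacy.

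This rests on three assumptions: the denominators of 25, 23 and 14 are inferred from percentages; 95% intervals and tests are taken as two-sided, which the plan does not state; and the identification of 0.025 with the three-group exact test is by numerical match, since the document does not say which test produced it. The choice among interval methods does not alter the conclusion.

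**What to change.** Add to the analysis and report in the Results:

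- **Main result:** the NAL minus self-directed difference in the proportion scoring B or better, with a score-based 95% confidence interval (Newcombe's is suitable). Base the efficacy conclusion on this, with the p-value for the same two-arm contrast in support.
- **Interpretation rule:** if the interval spans both benefit and harm, describe the result as inconclusive. This needs no margin, and the documents supply none.
- **Secondary results:** counts, differences and intervals for A or better and for failure, in the same two arms.
- **Labelling:** state that this is a post hoc correction made after the results were known, and that B or better was named as the main cut at that stage. It should not be presented as prespecified.

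The cost is a few sentences and some extra table entries from scores already collected. The downside is that the reported conclusion becomes visibly less precise.
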